
3.2 Design (including population, method, confounders and outcomes)

In March 2022, the first version of the survey was sent to 22 language schools in the Northern provinces and shared via various social media channels, such as the municipality of Groningen and the Foundation for Refugee Students (UAF). The survey included a digital questionnaire available in 17 languages (appendix 1), designed to collect data on professional background, curriculum vitae, credential evaluation, legal status, years of education and work experience, type of clinical experience, entrustable professional activities, and proficiency in Dutch, and English. The entrustable professional activities offer additional insights beyond traditional diploma evaluation.

Since December 2023, the REDCap recruitment process has been optimized (appendix 4) so that, in addition to skills, competencies are more broadly assessed to gain the best possible insight into the various domains identified by the World Economic Forum (WEF) as the most in-demand skills by organizations⁷. These include cognitive skills, self-efficacy, collaboration, ethics, physical skills, management skills, and technological skills. Based on the submitted

data, potential participants have been identified and invited for an application interview with the core team of the programme. Eligibility criteria include being a refugee or migrant residing in one of the three northern provinces with a nursing background, holding at least a diploma equivalent to the Dutch MBO-4 level, and having practical experience, preferably in a hospital setting. Additionally, candidates were required to demonstrate sufficient learning capacity to participate in a language course at the University of Groningen's Language Centre (LC). An intake at the LC is conducted before or shortly after the application interview to assess the candidate's developmental potential, considering factors such as motivation, initiative, intelligence, and communication skills. Throughout the course of the project, this intake was expanded to include a study skills test (appendix 5), a brief assessment designed to measure the speed at which an individual can learn a language. Candidates have been invited to participate if the LC deems the candidate's learning ability sufficient (based on the intake and, if available, a study skills test), and the application interview is successful.

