5.4 Inclusion and exclusion criteria

- Inclusion criteria:

- refugee or migrant with a nursing background or other paramedical background and sufficient indications that the relevant hospital department is prepared to cooperate in a fast-track integration trajectory
- holding at least a diploma equivalent to the Dutch MBO-4 level
- having practical experience, preferably in a hospital setting
- residence in one of the three northern provinces
- sufficient learning capacity to participate in a language course at the University of Groningen's Language Centre (LC) based on the intake and, if available, a study skills test
- a successful application interview

- Exclusion criteria:

- diploma lower than Dutch MBO-4 level
- refugee or migrant with a background as medical doctor

6. Study data, and analysis

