- Reason for rejection? different background than nursing; background as midwife/nurse where previous cases show insufficient experience in the nursing domain to participate in the newcomers program; has a nursing/caregiving background but does not have at least an MBO4 diploma equivalence; not sufficiently learnable according to language center / Study Skills Test; too little practical experience; practical experience too long ago; no status yet; residing outside regions participating in the newcomers program; language development not yet sufficient; may be considered later if appropriate language development is shown; too busy to participate in the program due to integration activities, searching for housing, etc.; other reason
- Living situation during the program? already own housing; medical vocational language program started from COA location, moved during the program to linked municipality; not residing at COA location or own housing, other
- Unlinked from previous municipality, linked to the municipality of Groningen? after obtaining status, linked to the municipality of Groningen within the program; unlinking from previously linked municipality, and linking to the municipality of Groningen within the program; already linked to a municipality near the hospital where the participant will start, within the newcomers program; not applicable
- reason for starting as a care assistant instead of assistant nurse (optionally indicate in which hospital as care assistant and where the participant may have worked as assistant nurse)
- Hospital name
- Type of department
- Extra guidance needed
- Type of additional support
- Cause of early dropout/ withdrawal
- Date of application received for a statement of professional competence for the nursing profession

 - Date of General Knowledge and Skills test - Date of profession-specific test 
Various durations are automatically calculated, including:
 
 - Working as an assistant nurse - From start as assistant nurse to date of profession-specific test - From date of profession-specific test to conditional BIG registration - Work under supervision - Internships - From start as assistant nurse to unconditional BIG registration - From start of medical vocational language program to date of early dropout - From start of medical vocational language program to start as assistant nurse 			

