Have all the data for the primary and secondary outcomes been described or the alternatives?	Yes 	No 	
6.2 Number of participants: Target total number of participants is estimated to fall within the range: 159-227 Target number of UMCG participants is estimated to fall within the range: 118-147			
6.3 Justification of sample size Based on the observed enrolment rates in the Northern region (3.3 participants per hospital per year) an additional 98 participants are expected to enrol between March 2025 and March 2031 if the 5 hospitals in this region continue to participate. Assuming a similar rate of enrolment in the Randstad, an additional 80 participants are expected in this period across the 4 hospitals located there. This results in a maximum of 227 participants across all hospitals during the entire study period. However, given potential risks such as hospitals discontinuing their participation due to lack of financial resources to cover 4–6 months of above-budget salary costs, a more conservative projection of approximately 30% fewer participants should be considered resulting in an estimated range of 159–227 participants. The sample size is therefore not based on a formal power analysis but on realistic projections of expected enrolment, as no official national data on the number of nursing newcomers are available. As such, the study follows a pragmatic design in which all eligible participants can enroll, depending on the availability of places in the hospitals involved in their region. This ensures that the sample is sufficiently large to answer the research questions regarding integration success, retention, and professional registration outcomes, while at the same time adhering to GDPR requirements to not include more participants than necessary.			
Has the sample size justification been described?	NA 	Yes 	No 

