Appendix 1:

To identify the number of nursing newcomers in the region interested in participating a questionnaire was developed in 2021 and processed using REDCap (Research Electronic Data Capture, Vanderbilt University). In addition to indicating whether someone was interested in participating, information could be provided on professional background, credential evaluation, legal status, years of education and work experience, type of clinical experience, entrustable professional activities, and proficiency in Dutch and English. The questionnaire was published in 16 different languages in addition to Dutch: English, French, Spanish, Persian, Farsi, Polish, Syrian Arabic, Kurdish, Ukrainian, Russian, Uzbek, Turkmen, Dari, Pashto, Bahasa Indonesia, and Turkish. It was disseminated online via a public survey link. In March 2022, the first version of the survey was sent to 22 language schools in the Northern provinces and shared via various social media channels, such as the municipality of Groningen, the Foundation for Refugee Students (UAF) and a national platform that supports connections between refugees and local communities, businesses, and organizations (RefugeeStartForce) with the following text: 'Possible job opportunity for asylum seekers or newcomers in the region of Groningen with a background as scrub nurse at an operating theater OR nurse at the nursing ward/ care unit. Are you interested to be guided to a job as a full team member at the operating theatre or nursing ward? In that case please click on the link below and fill in the form (3 minutes) on your smartphone or tablet:

www.redcap.link/nieuwkomers. Questionnaire in Dutch, English, Français, Español, زبان فارسی, Polski, العربية السورية, Kurdî, українська, русский, O'zbek, Türkmençe, دری, پښتو, Bahasa Indonesia, Türkçe.' The version available through this link is already an updated second version, after it became clear that there were enough potential participants to further shape the program. The questionnaire was updated a third time (December 2023) for scaling up to the other three Northern provinces and then a fourth time for scaling up to four hospitals in the Randstad which can be viewed via www.redcap.link/trajectnieuwkomers.

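### The inclusion criteria admit only residents of the three northern provinces, yet the enrolment target counts 80 participants from Randstad hospitals; as written, at most 147 people can be eligible against a stated range of 159–227.

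*Protocol*

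**What the plan says.** **Who may enter.** Section 5.4 lists, without qualification, "residence in one of the three northern provinces". Section 3.2 gives the same restriction when it describes eligibility as "being a refugee or migrant residing in one of the three northern provinces with a nursing background". Section 5.4 also asks for enough learning capacity to follow a course at the Groningen Language Centre, judged at intake and, where available, by a study skills test.

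**Who is counted.** Section 6.3 projects 98 further northern participants at five hospitals between March 2025 and March 2031. For the Randstad it adds that "an additional 80 participants are expected in this period across the 4 hospitals located there". It then states a maximum of 227 and, after a reduction of about 30%, a range of 159–227. Section 7.2.2.2 gives 49 participants as already enrolled. Appendix 1 describes the fourth update of the recruitment questionnaire as made for "scaling up to four hospitals in the Randstad".

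**A second residence rule.** Among the reasons for rejection in 6.1 is "residing outside regions participating in the newcomers program", which is wider than the criterion in 5.4.

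**Other totals.** Section 6.2 gives 118–147 as the UMCG target. Section 6.5d speaks of about 300 participants nationwide, 80 of them in the North.

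**The concern.** The eligibility section and the sample-size section cannot both be followed. A site that applies 5.4 literally turns away every applicant who lives in the Randstad, and the study then cannot reach any value in its stated range. A site that enrols them makes each one an eligibility deviation.

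The primary outcome is the proportion of participants who progress, complete the programme or move into care-assistant work. The set of people who count as participants therefore defines the estimate. If that is settled only after outcomes are known, the choice of denominator can be questioned, because Randstad hospitals may have different results from northern ones.

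**Working it through.** **Inputs**

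| Quantity | Value | Source |
|---|---|---|
| Already enrolled | 49 | 7.2.2.2 |
| Enrolment rate | 3.3 per hospital per year | 6.3 |
| Enrolment window | 6 years (March 2025 to March 2031) | 6.3 |
| Northern hospitals; expected additional participants | 5; 98 | 6.3 |
| Randstad hospitals; expected additional participants | 4; 80 | 6.3 |
| Reduction | about 30% | 6.3 |

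**1. Reproducing the protocol's figures**
- North: 3.3 × 5 × 6 = 99.0 (stated 98).
- Randstad: 3.3 × 4 × 6 = 79.2 (stated 80).
- Maximum: 49 + 98 + 80 = 227, as stated.
- Lower end: 0.70 × 227 = 158.9, that is 159, as stated.

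The 227 therefore contains the 80 Randstad participants, and the 30% cut is applied to the whole total, including those already enrolled.

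**2. Applying the residence criterion**
- Share ineligible at the maximum: 80/227 = 35.2%.
- Most that can be eligible: 49 + 98 = 147. This takes all 49 existing participants as northern; if some are not, the number is lower still.
- 147 is less than 159.

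**3. The share at the lower end.** Section 6.3 gives no regional split at 159, so 35% cannot simply be carried over.
- Proportional cut to everyone: 56/159 = 35.2%.
- Shortfall of 227 − 159 = 68 spread proportionally over the 178 new participants: 80 − 68 × 80/178 = 49.4, and 49.4/159 = 31%.
- Extremes: (80 − 68)/159 = 7.5% if all losses are in the Randstad, and 80/159 = 50.3% if all are in the North.

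**4. A northern-only range.** The answer depends on what the 30% is taken from.

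| Basis of the 30% cut | North only | All regions |
|---|---|---|
| Whole total (as in 6.3) | 0.70 × 147 = 102.9, i.e. 103 | 0.70 × 227 = 158.9, i.e. 159 |
| Future enrolment only | 49 + 0.70 × 98 = 117.6, i.e. 118 | 49 + 0.70 × 178 = 173.6, i.e. 174 |

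Setting 118 against 159 would mix the two bases. The pair 118 and 147 is also exactly what 6.2 prints as the UMCG target, although 147 is the total for all five northern hospitals.

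**5. Section 6.5d.** Its 80 northern participants are fewer than the 147 implied by 6.3, and its non-northern share would be (300 − 80)/300 = 73.3%.

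**6. Effect on precision.** The protocol gives no expected success proportion, so this uses assumed values. The 95% Wilson half-width is z√(p(1−p)/n + z²/4n²)/(1 + z²/n), with z = 1.96.

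| Assumed p | n = 227 | n = 147 |
|---|---|---|
| 50% | 6.5 points | 8.0 points |
| 75% | 5.6 points | 6.9 points |
| 90% | 3.9 points | 4.9 points |

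**The case against.** **The intent is visible, so this is only an outdated line.** The rejection reason in 6.1 refers to participating regions in general. Section 6.3 speaks of hospitals in the applicant's own region, and 6.5a describes the population as those enrolled at UMCG and partner hospitals. Section 3.2 is written largely as an account of past recruitment. All of this stands as evidence of what was probably meant. It does not amend 5.4, which is the operative list, and it leaves the protocol with two residence rules.

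**The Randstad belongs to the follow-up plan.** Section 4.5 does place national expansion after the pilot. But 6.3 counts the 80 within this study's own maximum, so this does not resolve the conflict.

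**The consequences are limited.** The study is descriptive and exploratory, and 6.3 says the size does not come from a power analysis. This stands: losing the Randstad widens the interval by only 1.0 to 1.5 points over the assumed proportions. The harm is an undefined population, not lost precision.

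**Stronger readings that the documents do not support**
- A reader might infer that the Groningen language criterion also bars Randstad applicants. It asks only for learning capacity. Completing the course is a programme step in Appendix 2, and Appendix 5 allows an online intake interview. The residence criterion alone carries the point.
- A reader might infer a full contradiction on professional background, because 5.4 admits a "refugee or migrant with a nursing background or other paramedical background" while 6.1 lists "different background than nursing" as a rejection reason. The latter is one option in a menu for recording why someone was turned down; it is not an eligibility rule and can apply to applicants with no paramedical background. Section 6.1 also codes background as nurse, nursing assistant or other, and foresees a comparable paramedical qualification at exit. What remains is the narrower nursing wording in 3.2.

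**Conclusion.** The contradiction holds and needs correction. The residence criterion in 5.4, repeated in 3.2, excludes a group that 6.3 counts towards the target: 35% of the maximum of 227. Under the criteria as written at most 147 participants can be eligible, so no value in the range 159–227 can be reached.

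This rests on two assumptions. Participants at Randstad hospitals are taken to live outside the three northern provinces; this is not stated, but 6.3 treats the two as separate regions. All 49 existing participants are taken as northern, which favours the protocol. The 35% applies to the maximum only; at 159 the share is not determined by the document.

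**What to change.** Choose one of two routes.

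1. **Include the Randstad.** In 5.4 and 3.2, replace the northern-province criterion with residence in a region that has a participating hospital, which matches the rejection reason already in 6.1. If Randstad applicants are assessed somewhere other than the Groningen Language Centre, adapt that criterion as well. Region can be derived from the hospital name, which 6.1 already records.
2. **Keep the northern criterion.** Restate the total in 6.2 and 6.3 as at most 147, remove the 80 Randstad participants, and say which basis the 30% cut uses: 103 if it applies to the whole total, as 6.3 does now, or 118 if it applies to future enrolment only.

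Under either route, correct or explain the 118–147 labelled as the UMCG target in 6.2, and bring the 300 nationwide and 80 northern in 6.5d into line with 6.3.

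A minor addition in the same amendment: align the nursing-background wording in 3.2 with the wider wording in 5.4.

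The cost is a short amendment of text, with no new data collection. Enrolment is projected to March 2031, so it is best made now, before more Randstad participants enter under a criterion that excludes them.

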6.1 Data collected

For primary outcomes:

- Background: nurse, nursing assistant, other
- Start date of medical vocational language program
- Start date as assistant nurse
- End date as assistant nurse
- Start date as care assistant
- Early dropout/ withdrawal
- In case of premature exit: 1 during (vocational) language training (months 3-6); 2 during early stages of the employment trajectory (months 7-12); 3 later in the employment trajectory (months 12-18/24)
- Date dropout/ withdrawal
- Date of decision on the application for a statement of professional competence and whether one may begin practicing under conditions
- CBGV decision on the application for a statement of professional competence: 1 decision granting a statement of professional competence allowing conditional registration in the BIG register ("Work in your profession in the Netherlands for three months under the supervision of a healthcare professional with the same profession who is fully registered in the BIG register, to become familiar with the Dutch healthcare system, related laws and regulations, and medical ethics.") Diploma is nearly equivalent. 2 additional internships: X months of internship in a hospital, VVT (nursing and care facilities), and/or GGZ (mental health care). 3 diploma not equivalent: Not allowed to practice as a nurse in the Netherlands.
- Conditional BIG registration date (above profession) with BIG number
- Date of possible meeting with the CIBG committee in case of a failing oral exam result, while results for the knowledge and practical tests are sufficient
- Start date of supervised practice
- End date of supervised practice
- Supervised practice: full-time, parttime
- In case of internships, what type of internships?
- Start date of internships

- End date of internships
- Internships: full-time, parttime
- Theoretical modules
- Knowledge test result: insufficient, sufficient, good
- Knowledge test score
- Profession-specific test result: insufficient, sufficient, good, excellent
- Oral examination result: insufficient, sufficient, good, excellent
- Date of issuance of the statement of professional competence, enabling the colleague to qualify for (unconditional) registration in the BIG register
- Date on which the participant is officially registered in the BIG register after submission and approval of CCPS and CGC, etc.
- Exit position: premature exit, exit as healthcare assistant, exit as BIG-registered nurse (or achievement of a comparable qualification at the paramedical level with a similar background)
- At exit: healthcare assistant or nurse – type of contract and number of hours: 1 Temporary (eg 1 year); 2 Permanent
- Start date as fully qualified nurse (possibly including onboarding period)
- Program underway and on track? program successfully completed; program still in progress and proceeding as planned; dropped out during the medical language program phase; dropped out during the assistant nurse phase due to insufficient background to continue; decided to stop BIG trajectory during assistant nurse phase and continue/start working as a care assistant; Other

For secondary outcomes and other outcomes:

Data to be completed by newcomer

- Years of education completed
- Country of training
- Attempts to have diploma recognized in the Netherlands
- Level achieved according to the diploma evaluation: A level that corresponds in Dutch terms to: diploma from senior secondary vocational education (MBO), qualification level 4, in nursing and care; 2 years of a nominal 4-year bachelor's program in higher professional education (HBO) in nursing; degree of bachelor in higher professional education (HBO) in nursing; degree of master in higher professional education (HBO) in nursing; other level
- Place of work experience: hospital, nursing home or care home, home care, other
- Years of work experience
- Last country you worked in before arriving in the Netherlands?
- Experience in the following types of hospital departments (multiple answers possible)
- Nursing tasks for which you are qualified: measuring blood pressure, wound care, removing stitches/sutures, preparing medication, venous puncture, inserting IV (intravenous) line, inserting urinary catheter, inserting nasogastric tube, resuscitation / CPR (cardiopulmonary resuscitation)
- As a nurse in the hospital, you have day, evening, and night shifts. Each shift lasts 8 hours. What is your attitude towards evening and night shifts? No problem, I am used to working these shifts; It will take some getting used to, but I think I can manage this with my private life; It is difficult to reconcile with my private life
- Years living in the Netherlands at time of entry
- Socioeconomic status at the time of entry
- Income level (if employed): 1 Less than or equal to minimum wage; 2 Comparable to a healthcare assistant's income; 3 Higher than a healthcare assistant's income
- Receiving healthcare allowance: 1 Yes; 2 No
- At entry EuroQol EQ-5D-5L questionnaire
- At exit EuroQol EQ-5D-5L questionnaire
- Residence and work permit for the Netherlands
- Basis for a residence permit? asylum; residence with partner; study (temporary residence permit); other

- Have you already had a 'Further Hearing' with the IND?
- Completed language/integration course?
- English/ Dutch language proficiency level: 1 A2 to B1; 2 B1 to B2; 3 B2
- Initials, surname, age, email address, phonenumber, current address or name of the shelter
- Domains: self-efficacy (resilience, flexibility, and adaptability; motivation and self-awareness; curiosity and lifelong learning; reliability and attention to detail); working with others (empathy and active listening; leadership and social influence); Ethics (cultural competence); physical skills (manual dexterity, endurance, and precision in the professional field); management skills (quality control); technological literacy (Appendix 4)
- Modified Racial Microaggressions Scale (RMAS) including 6 subscales: invisibility, criminality, dysfunctional culture, sexualization, foreigner/not belonging and environmental microaggressions. This questionnaire was developed by Torres-Harding et al⁸ and modified by King et al⁹ and appears to be an appropriate tool to assess this on the workplace¹⁰ (appendix 6).

Data to be completed by language center:

- Suitable candidate for 'Newcomers in Their Strength 2.0' program (based on intake)? No, the candidate is definitely unsuitable; yes, this is a suitable candidate; there is doubt about the candidate's suitability
- Score Study Skills Test
- Optional 2nd Score Study Skills Test
- Reason for taking 2nd Study Skills Test?

Data to be completed by study coordinator:

- Is the candidate a refugee or asylum seeker?
- Date of introductory meeting
- Candidate enrolled in newcomers program? no; yes; no, but may be considered in the future if the candidate develops appropriately
- Reason for rejection? different background than nursing; background as midwife/nurse where previous cases show insufficient experience in the nursing domain to participate in the newcomers program; has a nursing/caregiving background but does not have at least an MBO4 diploma equivalence; not sufficiently learnable according to language center / Study Skills Test; too little practical experience; practical experience too long ago; no status yet; residing outside regions participating in the newcomers program; language development not yet sufficient; may be considered later if appropriate language development is shown; too busy to participate in the program due to integration activities, searching for housing, etc.; other reason
- Living situation during the program? already own housing; medical vocational language program started from COA location, moved during the program to linked municipality; not residing at COA location or own housing, other
- Unlinked from previous municipality, linked to the municipality of Groningen? after obtaining status, linked to the municipality of Groningen within the program; unlinking from previously linked municipality, and linking to the municipality of Groningen within the program; already linked to a municipality near the hospital where the participant will start, within the newcomers program; not applicable
- reason for starting as a care assistant instead of assistant nurse (optionally indicate in which hospital as care assistant and where the participant may have worked as assistant nurse)
- Hospital name
- Type of department
- Extra guidance needed
- Type of additional support
- Cause of early dropout/ withdrawal
- Date of application received for a statement of professional competence for the nursing profession

 - Date of General Knowledge and Skills test - Date of profession-specific test 
Various durations are automatically calculated, including:
 
 - Working as an assistant nurse - From start as assistant nurse to date of profession-specific test - From date of profession-specific test to conditional BIG registration - Work under supervision - Internships - From start as assistant nurse to unconditional BIG registration - From start of medical vocational language program to date of early dropout - From start of medical vocational language program to start as assistant nurse 			
Have all the data for the primary and secondary outcomes been described or the alternatives?	Yes 	No 	
6.2 Number of participants: Target total number of participants is estimated to fall within the range: 159-227 Target number of UMCG participants is estimated to fall within the range: 118-147			
6.3 Justification of sample size Based on the observed enrolment rates in the Northern region (3.3 participants per hospital per year) an additional 98 participants are expected to enrol between March 2025 and March 2031 if the 5 hospitals in this region continue to participate. Assuming a similar rate of enrolment in the Randstad, an additional 80 participants are expected in this period across the 4 hospitals located there. This results in a maximum of 227 participants across all hospitals during the entire study period. However, given potential risks such as hospitals discontinuing their participation due to lack of financial resources to cover 4–6 months of above-budget salary costs, a more conservative projection of approximately 30% fewer participants should be considered resulting in an estimated range of 159–227 participants. The sample size is therefore not based on a formal power analysis but on realistic projections of expected enrolment, as no official national data on the number of nursing newcomers are available. As such, the study follows a pragmatic design in which all eligible participants can enroll, depending on the availability of places in the hospitals involved in their region. This ensures that the sample is sufficiently large to answer the research questions regarding integration success, retention, and professional registration outcomes, while at the same time adhering to GDPR requirements to not include more participants than necessary.			
Has the sample size justification been described?	NA 	Yes 	No 
